9.1.2. Method of Detecting AEs and SAEs

Care will be taken not to introduce bias when detecting AE and/or SAE. Open-ended and non-leading verbal questioning of the participant is the preferred method to inquire about AE occurrence.

9.1.3. Follow-up of AEs and SAEs

After the initial AE/SAE report, the investigators is required to proactively follow each participant at subsequent visits/contacts. All SAEs and non serious AEs of special interest (as defined in Section 3.3.1), will be followed until the event is resolved, stabilized, otherwise explained, or the participant is lost to follow-up (as defined in Section 8.3). Further information on follow-up procedures is given in Appendix 4.

9.1.4. Regulatory Reporting Requirements for SAEs

- Prompt notification by the investigators to the GSK of a SAE is essential so that legal obligations and ethical responsibilities towards the safety of participants and the safety of a study treatment under clinical investigation are met.
- GSK has a legal responsibility to notify both the local regulatory authority about the safety of a study treatment under clinical investigation. The GSK will comply with country-specific regulatory requirements relating to safety reporting to the regulatory authority, Institutional Review Boards (IRB), and investigators.
- Investigator safety reports must be prepared for suspected unexpected serious adverse reactions (SUSAR) according to local regulatory requirements and GSK policy and forwarded to principal investigator as necessary.
- An principal investigator who receives an investigator safety report describing a SAE or other specific safety information (e.g., summary or listing of SAE) from the GSK will review and then file it along with the IB and will notify the IRB, if appropriate according to local requirements.

9.1.5. Pregnancy

- Details of all pregnancies in female partners of male participants will be collected after the start of study treatment and until the follow-up visit.

- If a pregnancy is reported, the investigators should inform GSK within 24 hrs of learning of the pregnancy and should follow the procedures outlined in Appendix 5.
- Abnormal pregnancy outcomes (e.g., spontaneous abortion, fetal death, stillbirth, congenital anomalies, ectopic pregnancy) are considered SAE.

9.2. Treatment of Overdose

For this study, any dose of GSK2982772 greater than 720 mg within a 24-hr time period will be considered an overdose.

GSK does not recommend specific treatment for an overdose.

In the event of an overdose, the investigators should:

1. Contact the GSK Medical Monitor immediately.
2. Closely monitor the participant for AE/SAE and laboratory abnormalities until GSK2982772 can no longer be detected systemically (at least 2 days for GSK2982772).
3. Obtain a plasma sample for PK analysis if requested by the GSK Medical Monitor (determined on a case-by-case basis).
4. Document the quantity of the excess dose as well as the duration of the overdosing in the CRF.

Decisions regarding dose interruptions or modifications will be made by the investigators in consultation with the GSK Medical Monitor based on the clinical evaluation of the participant.

9.3. Safety Assessments

Planned time points for all safety assessments are provided in the SoA.

9.3.1. Physical Examinations

- A complete physical examination will include, at a minimum, assessments of the Skin, Cardiovascular, Respiratory, Gastrointestinal and Neurological systems. Height and weight will only be measured and recorded on screening.
- Investigators should pay special attention to clinical signs related to previous serious illnesses.

9.3.2. Neurological Examinations

Neurological examination will include, at a minimum, assessment of: mental status, gait, balance, coordination, cranial nerves, motor power, reflexes, and sensory system (light touch and pain). Assessments will be standardized across all scheduled time points (see SoA). Significant changes from the baseline or any clinically significant changes will be noted as part of further scheduled examinations or unscheduled examinations (if needed).

Clinically significant abnormalities or changes in status from baseline will be:

- entered as an adverse event,
- may trigger increased monitoring of the subject(s),
- may result in withdrawal of the subject (see Section 8.2),
- may result in referral to a specialist.

9.3.3. Vital Signs

- Axillary temperature, pulse rate, and blood pressure will be assessed.
- Blood pressure and pulse measurements will be assessed supine position with a completely automated device. Manual techniques will be used only if an automated device is not available.
- Blood pressure and pulse measurements should be preceded by at least 5 minutes of rest for the participant in a quiet setting without distractions (e.g., television, cell phones).
- Vital signs will be measured in a supine position after 5 minutes rest and will include temperature, systolic and diastolic blood pressure, and pulse rate.

9.3.4. Electrocardiograms

- Single 12-lead ECG will be obtained as outlined in the SoA (see Section 2) using an ECG machine that automatically calculates the heart rate and measures PR, QRS, QT, and QTcF intervals. Refer to Section 8.1.3 for QTc withdrawal criteria and additional QTcF readings that may be necessary.
- Single ECGs will be obtained at each time point.
- If QTcF is appeared the value applied the discontinuation criteria, ECG must be conducted two additional readings and be confirmed whether apply the discontinuation criteria.
- Continuous cardiac telemetry will be performed at time points indicated in the SoA (see Section 2). Full disclosures will be reviewed in detail and the review maintained as part of the subject's source documents.

9.3.5. Clinical Safety Laboratory Assessments

- Refer to Appendix 2 for the list of clinical laboratory tests to be performed and to the SoA for the timing and frequency.
- The investigators must review the laboratory report, document this review, and record any clinically relevant changes occurring during the study in the AE section of the CRF. The laboratory reports must be filed with the source documents. Clinically significant abnormal laboratory findings are those which are not associated with the underlying disease, unless judged by the investigators to be more severe than expected for the participant's condition.

- All laboratory tests with values considered clinically significantly abnormal during participation in the study should be repeated until the values return to normal or baseline or are no longer considered significantly abnormal by the investigators or GSK Medical Monitor.
- If such values do not return to normal/baseline within a period of time judged reasonable by the investigators, the etiology should be identified and the GSK notified.
- All protocol-required laboratory assessments, as defined in Appendix 2, must be conducted in accordance with the laboratory manual of study site and the SoA.

9.3.6. Suicidal Risk Monitoring

GSK2982772 is considered to be a CNS-active drug. There is some concern that some CNS-active drugs may be associated with an increased risk of suicidal thinking or behaviour when given to some subjects. Although this drug has not been shown to be associated with an increased risk of suicidal thinking or behaviour when given to healthy volunteers, GSK considers it important to monitor for such events before or during clinical studies with compounds such as this.

Participants being treated with GSK2982772 should be monitored appropriately and observed closely for SIB or any other unusual changes in behaviour. All subjects who experience signs of suicidal ideation or behaviour must immediately be discontinued from study medication.

Families of participants being treated with GSK2982772 should be alerted about the need to monitor participants for the emergence of unusual changes in behaviour, as well as the emergence of SIB and to report such symptoms immediately to the study investigators.

9.4. Pharmacokinetics

- Blood samples of approximately 2 mL will be collected for measurement of plasma concentrations of GSK2982772 as specified in the SoA. Instructions for the collection and handling of biological samples will be described in the SRM. The actual date and time (24-hr clock time) of each sample will be recorded.
- Samples will be used to evaluate the PK of GSK2982772. Samples collected for analyses of GSK2982772 plasma concentration may also be used to evaluate safety aspects related to concerns arising during or after the study.

Drug concentration information that may unblind the study will not be reported to investigative sites or blinded personnel until the study has been unblinded.

9.5. Genetics

In this study, genetics may be evaluated after review by the ethical review committee established by GSK in accordance with Japanese ethical guidelines for human genome/gene analysis research.

A 6 mL blood sample for DNA isolation will be collected from participants who have consented to participate in the genetics analysis component of the study. Participation is optional. Participants who do not wish to participate in the genetic research may still participate in the study.

In the event of DNA extraction failure, a replacement genetic blood sample may be requested from the participant. Signed informed consent will be required to obtain a replacement sample unless it was included in the original consent.

See Appendix 6 for Information regarding genetic research. Details on processes for collection and shipment and destruction of these samples can be found in SRM.

10. STATISTICAL CONSIDERATIONS

The objectives of this study are to evaluate safety, tolerability and PK of GSK2982772 in healthy Japanese subjects. No formal statistical hypotheses will be tested. Descriptive statistics will be used to assess safety and tolerability. An estimation approach will be used to address the pharmacokinetic study objectives, where point estimates and corresponding confidence intervals (CI) will be constructed.

10.1. Sample Size Determination

In a 4-way crossover design, total 12 subjects will be randomized in four groups with a randomization ratio of 1:1:1:1; 3 subjects in each group. The sample size for this study is based on the feasibility rather than statistical considerations. The number of subjects who will take a placebo, 60 mg, 120 mg, or 240 mg dose will be 12 with totalizing four groups. No calculations for formal power and sample size are performed.

One of the objectives of this study is safety, where a number of safety events are of interest. A maximum of 12 subjects will receive each active dose and; therefore, if 0/12 of a particular safety event in the GSK2982772 group is observed, the upper limit of the exact 95% CI indicates that a true incidence rate of 26.5% could not be ruled out. Whereas if 1/12 of the same safety event in the GSK2982772 group is observed, the upper limit of the exact 95% CI indicates that a true incidence rate of 38.5% could not be ruled out.

Using a Bayesian approach to determine the CI around an observed safety event, we would assume a flat Beta (1, 1) prior, and if we were to observe one safety event in 12 then the posterior distribution would be Beta (2, 12), as outlined in Figure 1. Thus, we can 95% certain that the true probability of the safety event lies between 0.02 and 0.36.

[figure not shown]

Figure 1 Bayesian Approach to Determine Confidence in Safety Event

Between-subject variability of C_{max} and AUC(0-t) of GSK2982772 is estimated to be 32.9% (CV%) and 23.5% (CV%), respectively (based on PK results of 60 mg BID on Day 1 and 120 mg BID on Day1 from Study 200975 Part B). Based on these variability estimates and the sample size of 12, the upper limit value of 95% CI of geometric mean of C_{max} and AUC(0-t) is estimated to be approximately 22.6% and 15.9%, respectively.

10.2. Sample Size Sensitivity

Different safety event rates were investigated for sample size sensitivity analysis. If the number of subjects who completed each active dose was different, then the true incidence rates of safety events that could not be ruled out would change. These changes are outlined as below.

Completed N	Number of a particular safety event observed with GSK2982772	Upper limit of exact 95% CI indicating that a true incidence rate of x% could not be ruled out
12	2	48.4%
	3	57.2%
	4	65.1%
11	0	28.5%
	1	41.3%
	2	51.8%
	3	61.0%
10	0	30.8%
	1	44.5%
	2	55.6%
	3	65.2%

Following table shows how the results could have variabilities with changing between-subject estimates of variability (CV%) and number of subjects. Estimates of the upper limit values of 95% CI of geometric mean are described using proportions (%) of variability to geometric mean of PK parameters.

N	Estimate of between-subject variability (CV%)			
	20	30	40	50
11	14.2%	21.8%	29.5%	37.3%
12	13.4%	20.5%	27.7%	35.0%
13	12.7%	19.4%	26.2%	33.0%
14	12.1%	18.4%	24.9%	31.4%

10.3. Populations for Analyses

For purposes of analysis, the following populations are defined:

Population	Description
Screened	All subjects who have a screening visit will be included.
Enrolled	All subjects who passed screening and entered the study will be included. Note screening failures (who never passed screening even if rescreened) and subjects screened but never enrolled into the study (Reserve, Not Used) are excluded from the Enrolled population as they did not enter the study.

Population	Description
Safety analyses	All subjects who have received at least one dose of study treatment will be included. This population will be used for the safety analyses.
PK analyses	All subjects in the Safety population for whom a PK sample has been obtained and analyzed will be included. This population will be used for the PK analyses.

10.4. Statistical Analyses

10.4.1. Safety Analyses

All safety analyses will be performed on the Safety Population. Safety data will be presented in tabular and/or graphical format and summarized descriptively according to GSK's Integrated Data Standards Library (IDSL) standards.

The tables, figures, and listings will use the Safety Population unless otherwise specified. AEs, changes in clinical laboratory values, 12-Lead ECGs, findings during continuous cardiac telemetry and vital signs will be summarized by dose group (i.e. placebo, 60 mg, 120 mg, and 240 mg) to assess the safety and tolerability of GSK2982772. The safety and tolerability results will not to be formally compared between each group and comparison with placebo will be based on review of descriptive summaries.

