5.6. Scientific Rationale for Study Design

This study will include a placebo control study, to allow for evaluation of AEs attributable to treatment versus those independent of treatment.

In Study 200975, 67 subjects were exposed to active treatment. GSK2982772 was well-tolerated, with no deaths or other non-fatal SAEs being reported. Sentinel dosing approach was taken in Study 200975, where two subjects receive placebo or GSK2982772 on Day 1 and the remaining subjects are dosed after safety evaluation at 24 hrs of preceding two subjects. Since this study is the first study in Japanese subjects, this study adopts a cautious approach including sentinel dosing and will include rigorous safety monitoring to confirm the safety profile prior to dose-escalation of single dose of the next dose strength, which was the same way taken in the past non-Japanese study.

In the 4 week repeat dose nonclinical toxicology studies, neurological related events (uncoordinated movement, irregular gait, trembling, hunched appearance and decreased activity) were observed in some rats and monkeys. On the other hand, in the 13 week repeat dose nonclinical toxicology studies in rats or monkeys, or in the 39 week repeat dose nonclinical toxicology study in monkeys, no neurological-related events were observed in rats or monkeys. There have been some reports of lethargy, abnormal dreams, and depressed mood in Study 200975 (See IB for GSK2982772 [GlaxoSmithKline Document Number 2014N204126_04]). This study includes neurological exams by considering these findings from Study 200975.

In the currently ongoing non-Japanese healthy volunteer study (Study 205184) being conducted in the United Kingdom (UK), several asymptomatic arhythmias were detected in 6 out of 25 subjects treated with GSK2982772 or placebo. The study was temporarily

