7.2. Method of Treatment Assignment

On Day 1, participants will be assigned a unique number (randomization number) in ascending numerical order. The randomization number encodes the participant's assignment to one of the 4 groups, according to the randomization schedule generated prior to the study by the Biomedical Data Sciences Department at GSK. Each participant will be dispensed blinded study treatment, labelled with his unique randomization number, throughout the study.

Subjects will be randomized to one of four sequences (A, B, C and D), where the treatments in the sequences are:

- A: Placebo TID / 60 mg TID / 120 mg TID / 240 mg TID
- B: 60 mg TID / Placebo TID / 120 mg TID / 240 mg TID
- C: 60 mg TID / 120 mg TID / Placebo TID / 240 mg TID
- D: 60 mg TID / 120 mg TID / 240 mg TID / Placebo TID

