#### 7.1.1. Details of Planned Adverse Events Summaries

##### Adverse Events (AEs)

###### All AEs by SOC and PT

The number and percentage of subjects with all relevant adverse events will be summarized by MedDRA System Organ Class and Preferred Term by treatment group. The counting of events and the percentages will be based on the number of subjects on each treatment, so subjects may appear in more than one treatment category.

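### Dose rises with period, but the adverse-event and telemetry summaries pool each treatment over periods, so only half of the placebo records are concurrent with 60 mg or with 240 mg and a steady background trend would bias both comparisons

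*Protocol*

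**What the plan says.** Protocol 5.6 gives the purpose of the placebo arm as "to allow for evaluation of AEs attributable to treatment versus those independent of treatment". Protocol 7.2 lists four sequences. The first is "A: Placebo TID / 60 mg TID / 120 mg TID / 240 mg TID". The other three keep the active doses in the same ascending order and move placebo to the second, third and fourth period in turn. Protocol 10.1 fixes the numbers: "total 12 subjects will be randomized in four groups with a randomization ratio of 1:1:1:1; 3 subjects in each group".

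Protocol 10.4.1 summarises safety in four columns (placebo, 60, 120 and 240 mg), with no formal comparison; "comparison with placebo will be based on review of descriptive summaries". SAP 7.1.1 follows this for adverse events: "The counting of events and the percentages will be based on the number of subjects on each treatment". SAP 7.3.1 does the same for telemetry results and for specific telemetry abnormalities. In SAP Appendix 9, Tables 2.1 to 2.4 (adverse events) and 2.18 and 2.19 (telemetry) have no by-period version.

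The period is nevertheless available. SAP 9.3.1 assigns each assessment to a period, and SAP 9.3.1.1 assigns each adverse event to one. No planned adverse-event or telemetry summary is described as using it. SAP 5.3.1 names no stratum for safety and refers only to the PK model.

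**The concern.** The three active doses are never randomised in order. What is randomised is the period in which a man takes placebo. The concurrent randomised comparison is therefore between the 3 men on placebo in a given period and the 9 on drug in that period. The planned columns mix periods in different proportions: placebo evenly, 60 mg mostly from Period 1, 240 mg mostly from Period 4.

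If background events become more common over repeated confinements, 60 mg looks better than placebo and 240 mg looks worse, which resembles a dose response. If they fade after the first confinement, the pattern reverses and a real effect at 240 mg could be masked. Separating drug events from background is the stated reason for having placebo, and 240 mg TID is the top of the range meant to support Phase 2b, so these are the contrasts that readers will look at most.

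**Working it through.** **Inputs.** The four sequences (Protocol 7.2) and 3 men per sequence (Protocol 10.1), assuming that all 12 complete.

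**Step 1: exposures by period.**

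| Column | P1 | P2 | P3 | P4 | Total | Mean period |
|---|---|---|---|---|---|---|
| Placebo | 3 | 3 | 3 | 3 | 12 | 2.50 |
| 60 mg | 9 | 3 | 0 | 0 | 12 | 1.25 |
| 120 mg | 0 | 6 | 6 | 0 | 12 | 2.50 |
| 240 mg | 0 | 0 | 3 | 9 | 12 | 3.75 |

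The totals reproduce the 12 per treatment stated in Protocol 10.1. The exact 95% upper limit for 0/12 also reproduces: 1 - 0.025^(1/12) = 26.5%.

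**Step 2: concurrent placebo.** 60 mg is given only in Periods 1 and 2, which hold 3 + 3 = 6 of the 12 placebo records. 240 mg is given only in Periods 3 and 4, which hold the other 6.

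**Step 3: bias with no drug effect.** Let b1 to b4 be the background percentages in Periods 1 to 4. The expected difference is the sum over periods of (n_dose,p/12 - 3/12) × b_p:

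- 60 mg minus placebo: 0.5·b1 - 0.25·b3 - 0.25·b4
- 120 mg minus placebo: -0.25·b1 + 0.25·b2 + 0.25·b3 - 0.25·b4
- 240 mg minus placebo: -0.25·b1 - 0.25·b2 + 0.5·b4

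For a linear trend of d points per period, the bias is d times the difference in mean period:

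- 60 mg: (1.25 - 2.50)d = -1.25d
- 120 mg: (2.50 - 2.50)d = 0
- 240 mg: (3.75 - 2.50)d = +1.25d

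**Step 4: patterns.** The background rates are assumed, because the documents give none.

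| Background, P1 to P4 | Placebo | 60 mg | 120 mg | 240 mg |
|---|---|---|---|---|
| flat, 20% throughout | 20% | 20% | 20% | 20% |
| 5/10/15/20% | 12.5% | 6.25% | 12.5% | 18.75% |
| 40/30/20/10% | 25% | 37.5% | 25% | 12.5% |
| 30/10/10/10% | 15% | 25% | 10% | 10% |
| 30/10/10/30% | 20% | 25% | 10% | 25% |

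A flat background gives no bias. A single-period shift biases all three contrasts, including 120 mg (10% - 15% = -5 points). The symmetric pattern cancels between 60 and 240 mg, although each still differs from placebo.

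**Step 5: what matching by period leaves.** Placebo reweighted to the periods of 60 mg (0.75 Period 1, 0.25 Period 2) has an effective number of 1/[(0.75² + 0.25²)/3] = 4.8 men. The figure is the same for 240 mg, and for 120 mg it is 1/[(0.5² + 0.5²)/3] = 6.

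**The case against.** The strongest reply is that nothing in the documents shows a trend, and that the study could hardly resolve one. One man is 1/12 = 8.3 points of a column, so the bias against placebo reaches one man only at d = 8.3/1.25 = 6.7 points per period. Nothing is formally tested, and 0/12 already leaves 26.5% open. A within-period placebo cell with 0/3 events has an exact 95% upper limit of 1 - 0.025^(1/3) = 71%. All of this stands. It limits what the extra tables can show and makes them supportive.

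Second, placebo is balanced over periods and each man is his own control. That is true, and it removes any difference in who contributes to each column. It does not remove the difference in when they contribute.

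Third, the information is retained. Listing 14 gives every adverse event, and Listing 5 gives planned and actual treatments. For adverse events, a reader could rebuild the period view by hand. For telemetry this fails: Listing 33 holds only clinically significant abnormalities, so the remaining abnormal findings are planned only as pooled counts. The end-of-period reviews work on blinded data (Protocol 5.4) and serve escalation, not the final comparison with placebo.

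Fourth, the standard table shells are not reproduced in the SAP, so the absence of a by-period display is read from its text and titles. That caveat stands.

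**Conclusion.** The point holds as a gap in the final summaries, not in the data collected. Under a steady background trend of d points per period, with all 12 men completing, the pooled columns bias 60 mg minus placebo by -1.25d and 240 mg minus placebo by +1.25d. The actual size is unknown because d is unknown.

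Four stronger readings are tempting, and the documents do not support them.

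- A reader might infer that any period trend looks like a dose effect. A linear trend leaves 120 mg minus placebo unbiased, symmetric patterns can cancel between 60 and 240 mg, and a falling trend runs inverse to dose.
- A reader might infer that placebo is not a concurrent control at all. Half of its records are concurrent with 60 mg and half with 240 mg.
- A reader might take the arrhythmias in Study 205184 (6 of 25 men, Protocol 5.6) as evidence of drift. That figure covers men on drug or placebo, is not split by period, and the cardiac panel called the events random in occurrence.
- A reader might infer that a difference adjusted for subject and period is needed. Least squares on this design raises the standard error of dose minus placebo from 0.408 to 0.494 residual SD for 60 and 240 mg, and to 0.447 for 120 mg. For 240 minus 60 mg it goes from 0.408 to 0.667, which is 63% larger. With 3 placebo men per period and no stated model for sparse binary events, that exchange of bias for variance is debatable, and it is not requested here.

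**What to change.** In SAP 7.1.1 and 7.3.1, and in the table list in Appendix 9:

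- Add treatment-within-period versions of Table 2.1 (all adverse events), Table 2.3 (drug-related adverse events) and Table 2.19 (telemetry abnormalities), using the period assignment in SAP 9.3.1 and 9.3.1.1.
- Keep the pooled columns. State that the descriptive comparison with placebo is also read against the men on placebo in the same periods: Periods 1 and 2 for 60 mg, 2 and 3 for 120 mg, 3 and 4 for 240 mg.

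The cost is a few sentences and three tables from data already classified by period, with no new data and no change in conduct. The downside is sparseness: with 3 men in each placebo cell, many entries will be 0 or 1, and the text should say that these tables support the pooled summaries and do not replace them.
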